6.8.3.1.	Non-serious Adverse Events.....	60
6.9.	Pregnancy.....	61
6.9.1.	Follow-up.....	62
6.10.	Immune-related Adverse Events.....	62
6.11.	Rapid Notification of Adverse Events of Special Interest.....	63
6.12.	Medical Monitoring.....	63
6.12.1.	Data and Safety Monitoring Committee.....	64
6.12.2.	Efficacy.....	64
6.14.	Other Safety Considerations.....	64
7.	Data handling and record keeping.....	64
7.1.	Confidentiality Regarding Study Subjects.....	64
7.2.	Confidentiality and HIPAA.....	65
7.3.	Source Documentation.....	65
7.4.	Data and Source Documentation.....	65
7.5.	Recording of Data and Retention of Documents.....	66
8.	STUDY MONITORING, AUDITING AND INSPECTING.....	66
8.1.	Study Monitoring Plan.....	66
8.2.	Auditing Procedure.....	68
9.	Ethical aspects.....	68
9.1.	Ethics and Good Clinical Practice.....	68
10.	Study Finances.....	68
10.1.	Funding Source.....	68
10.2.	Subject Stipends or Payments.....	68
11.	Publication plan.....	68
12.	administrative requirements.....	69

12.1. Institutional Review Board	69
12.2. Protocol Amendments.....	69
13. REFERENCES.....	70
14. APPENDICES.....	73
Appendix 1: Imaging Methodologies	74
Appendix 2: ECOG Performance Status.....	75
Appendix 3: Pre-existing Autoimmune Diseases	76
Appendix 4: Description of Use of Blood Samples for Immune Analyses	77

SYNOPSIS

TITLE

A Pilot Trial of Ipilimumab with NIVOLUMAB for Patients with Resected Stages IIIB/IIIC/ IV Melanoma

PROTOCOL NUMBERS

S16-00098 (Perlmutter Cancer Center)

CA209-905(Bristol-Myers Squibb Co.)

OBJECTIVES

The primary objective of this study is to assess the safety and tolerability of treatment with NIVOLUMAB in combination with ipilimumab in HLA unrestricted subjects with resected Stages IIIB/IIIC/IV melanoma.

The secondary objectives of this study are to:

- evaluate the immune response to treatment with the study drugs at Week 12
- assess the preliminary efficacy of the study drugs as measured to time to relapse.

OVERVIEW OF STUDY DESIGN

This is a pilot, phase II, open-label, single center study of NIVOLUMAB in combination with ipilimumab. NIVOLUMAB is an FDA-approved fully human monoclonal antibody (HuMAb) against programmed death-1 (PD-1). (See STUDY DRUGS, DOSES, AND ADMINISTRATION). Ipilimumab is a FDA-approved fully human monoclonal antibody against cytotoxic T lymphocyte antigen-4 (CTLA-4)

The study will consist of 4 periods: Screening (up to 4 weeks), Induction Treatment (up to 1 12-week cycle of induction therapy with ipilimumab and NIVOLUMAB), Treatment/Follow-up (up to 48 weeks of NIVOLUMAB), and Survival Follow-up. Each induction treatment cycle is comprised of 4 doses of NIVOLUMAB and 4 doses of ipilimumab given every three weeks for a total of 12 weeks (cycle 1) with a tumor assessment at the end of cycle 1 at week 12.

At the end of the Induction Treatment Period (Week 12) subjects without evidence of relapse radiologically and clinically will be able to continue to receive NIVOLUMAB treatment 480mg every 4 weeks for 48 weeks. Subjects who relapse at the disease evaluations at Weeks 12, 24 or later will not receive further treatment with NIVOLUMAB.

Patients who experience a DLT to NIVOLUMAB and ipilimumab during or after cycle 1 will not receive further treatment with NIVOLUMAB and ipilimumab.

Subjects who prematurely discontinue 1 or both study drugs will complete the remaining study visits and associated evaluations (without dosing of 1 or both study drugs, as applicable) indefinitely until withdrawal of consent for follow-up or death.

Dosing during cycle 1 will consist of: 3 mg/kg of NIVOLUMAB + ipilimumab at 1 mg/kg

Dosing during cycles 2-5 will consist of flat dose NIVOLUMAB at 480 mg

Since the drugs will be given concurrently, it will not be possible to attribute dose-limiting toxicities to one or the other drug during the first 12 weeks of therapy.

Subjects who withdraw from the study during Cycle 1 for reasons other than a DLT will be replaced.

No dose escalations or de-escalations are permitted within each subject's treatment. NIVOLUMAB or ipilimumab dose adjustments are allowed only if there has been $\pm 10\%$ weight change since the previous treatment (Induction/Treatment Period only). No dose escalations or de-escalations are allowed during cycles 2-5 due to the use of flat dosing of NIVOLUMAB at 480 mg every 4 weeks.

NUMBER OF SUBJECTS (PLANNED)

Up to 25 subjects (20 in this trial with five to account for drop-outs) will be enrolled in the study.

BLINDING AND RANDOMIZATION

This is an open-label study. Eligible subjects will be treated in the order they enter the study.

DIAGNOSIS AND MAIN CRITERIA FOR INCLUSION

Subjects will have no HLA restriction, and have a histological diagnosis of Stages IIIB/IIIC/IV Melanoma that has been completely resected, rendering them free of disease.

STUDY DRUGS, DOSES AND MODE OF ADMINISTRATION

NIVOLUMAB will be supplied as a sterile, preservative-free solution in 10 mL vials at a concentration of 10 mg/mL; which, in cycle 1, based on the subject's weight, may be diluted with sterile normal saline (0.9% sodium chloride). NIVOLUMAB (3 mg/kg) will be administered as a 30-minute i.v. infusion.

Starting 4 weeks after the last co-administered dose in cycle 1, subjects will be administered a flat dose 480 mg nivolumab IV every 4 weeks (Q4W) in cycles 2-5.

Ipilimumab will be supplied as a sterile, preservative-free solution in 10mL (50 mg) or 40 mL (200 mg) vials at a concentration of 5 mg/mL; which, based on the subject's weight, may be diluted with sterile normal saline (0.9% sodium chloride). Ipilimumab (1 mg/kg) will be administered as a 30-minute i.v. infusion.

On days when both study drugs are administered, nivolumab (BMS-936558) will be given before the ipilimumab.

DURATION OF TREATMENT/STUDY PARTICIPATION

The expected maximum duration of nivolumab treatment for a subject is 60 weeks. The expected maximum duration of ipilimumab treatment for a subject is 12 weeks.

The expected maximum duration of a subject's participation in this study is 3 years.

CRITERIA FOR EVALUATION

Safety

Evaluation of safety and tolerability will include ongoing review of clinical laboratory tests (blood and urine sampling for clinical laboratory parameters), pregnancy testing, Eastern Cooperative Oncology Group (ECOG) performance status, physical examination including vital sign measurements, electrocardiogram (ECG), chest radiography, and adverse events. Safety will also include evaluations of immune safety and immunogenicity.

Dose-limiting Toxicity

A DLT is defined as a NIVOLUMAB and/or ipilimumab-related \geq Grade 3 adverse event occurring within 29 days after the first dose of study drugs excluding: Grade 3 adverse event of tumor flare (defined

as local pain, irritation, or rash localized at sites of known or suspected tumor), Grade 3 rash, Grade 3 immune-related adverse event (irAE, defined below) that resolves to a Grade 1 or less within 28 days, or a transient (resolving within 6 hours of onset) Grade 3 infusion-related adverse event. A Grade 3 irAE that resolves to a Grade 1 or less within 28 days, while not constituting a DLT, may preclude further administration of NIVOLUMAB or NIVOLUMAB with ipilimumab to the subject. Grade 2 irAEs may require skipping a dose unless resolved to grade 1 or less at the time of drug administration. Version 4.0 of the NCI Common Terminology Criteria for Adverse Events (CTCAE) will be utilized for AE reporting. Version 4.0 of the CTCAE is identified and located on the CTEP website at http://ctep.cancer.gov/protocolDevelopment/electronic_applications/ctc.htm. All appropriate treatment areas should have access to a copy of Version 4.0 of CTCAE).

Toxicities occurring more than 28 days after the first dose will be monitored and discussed with BMS.

Immune-Related Adverse Events

An irAE is defined as a clinically significant adverse event of any organ that is associated with either study drug exposure, of unknown etiology, and is consistent with an immune-mediated mechanism. Appropriate efforts should be made to rule out neoplastic, infectious, metabolic, toxin, or other etiologic causes of the irAE.

Given the intended mechanism of action of NIVOLUMAB and ipilimumab, particular attention will be given to adverse events that may follow enhanced T-cell activation such as dermatitis and colitis, or other irAEs.

Immunology

Blood and peripheral blood mononuclear cell samples will be collected and evaluated by leukapheresis or peripheral blood draw for flow cytometry (T cell, B cell, NK, monocytes, CD3, CD4, CD8, CD4/CD8, CD11b, CD11c, CD14, CD20, CD25, CD33, CD56, CD69, CD71, CD73, CD80, CD127, FOXP3, LAG3, TIGIT, BTLA, Tim3, CTLA-4, PD-1, PD-L1, CD244, OX-40, 41-BB, CD40, CD4/MHC Class II positive cells, and CD8/MHC Class II positive cells), serum cytokines (IL-6, IL-10, TNF- β , ING-gamma, TGF- β , neopterin and sIL-2R), cellular immune function (tetramer and/or ELISpot assays utilizing melanoma and other control antigens).

Serum samples will be collected and cryopreserved to study molecules that may be implicated in regulating anti-melanoma immune responses and/or NIVOLUMAB or ipilimumab activity such as soluble MICA, compounds detected by mass spectroscopy including those associated with wound healing, complement and the acute phase response, chemokines or cytokines, or antibodies to melanoma antigens.

Efficacy

Using imaging results (computed tomography/magnetic resonance imaging [chest, abdomen, pelvis, and brain] and photography of lesions) as well as clinical examination, presence of relapse will be evaluated and treatment decisions will be made by the Investigator (who is also the Sponsor). Scans and measurements may be reviewed by independent radiologists at a later date or any time during the study.

The primary efficacy endpoint is relapse free survival as determined by the results of Investigator evaluations.

STATISTICAL METHODS

A sample size of up to 20 subjects with 5 additional patients to accommodate drop-outs is based on the study design for safety evaluation requirements.

The incidence, relationship to therapy, and severity of adverse events will be summarized using descriptive statistics. Changes in clinical laboratory tests, ECOG, vital signs, ECGs, chest radiography, and immune safety results will be summarized using descriptive statistics. Immunogenicity results will be provided as a listing.

Immune response will be summarized using descriptive statistics..

Efficacy evaluations (RFS) will be summarized using descriptive statistics.

ABBREVIATION

Abbreviation	Term
β-HCG	beta human chorionic gonadotropin
AIDS	acquired immunodeficiency syndrome
ALT	alanine aminotransferase
APC	antigen-presenting cells
AST	aspartate aminotransferase
BMS	Bristol-Myers Squibb
BOR	Best Overall Response
BORR	Best Overall Response Rate
CI	confidence interval
CR	Complete Response
CRF	case report form
CTCAE	Common Terminology Criteria for Adverse Events
CTEP	Cancer Therapy Evaluation Program
CTLA-4	cytotoxic T lymphocyte-associated antigen 4
DC	dendritic cells
DLT	dose-limiting toxicity
DNA	deoxyribosenuclelic acid
ECG	electrocardiogram
ECOG	Eastern Cooperative Oncology Group
ESI	event of special interest
FDA	Food and Drug Administration
GCP	Good Clinical Practice
GI	Gastrointestinal
HBV SAg	hepatitis B virus surface antigen
HCV RNA	hepatitis C virus ribonucleic acid
HIV	human immunodeficiency virus
HPF	high power field
HuMAb	human monoclonal antibody
i.v.	intravenous, intravenously
ICF	informed consent form
ICH	International Conference on Harmonisation
IL-2	interleukin-2
INF	Interferon
irAE	Immune-related adverse event
IRB	Institutional Review Board
irCR	Immune-related complete response
irPD	Immune-related progressive disease
irPR	Immune-related partial response

Abbreviation	Term
irRC	Immune-related Response Criteria
irSD	Immune-related stable disease
mAb	monoclonal antibody
NIVOLUMAB	PD-1-specific, fully human IgG4 mAb
MedDRA	Medical Dictionary for Regulatory Activities
mWHO	Modified World Health Organization
MPR	Mixed Lymphocyte Reaction
MTD	maximum tolerated dose
NCI	National Cancer Institute
PBMC	peripheral blood mononuclear cells
PCC	Perlmutter Cancer Center
PD-1	Programmed Death-1
PD-L1	Programmed Death-Ligand 1
PI	Propidium Iodide
PR	Partial Response
PVG	Pharmacovigilance
SAE	serious adverse event
RECIST	Response Evaluation Criteria in Solid Tumors
SOC	system/organ/class
SOP	standard operating procedure
SPD	Sum of Product Diameters
SSAE	Serious or Significant Adverse Event
TEAE	treatment-emergent adverse event
TNF	tumor necrosis factor
ULN	upper limit of normal
URTI	upper respiratory tract infection
US	United States of America
UTI	urinary tract infection
WBC	white blood cell
WHO	World Health Organization

TABLE 1: TIME AND EVENTS SCHEDULE

Examination	Screening	Cycle 1 Treatment Period ^{11, 13} (Visits must occur ± 7 days of the scheduled visit)					Cycle 2-5 Treatment Period ^{11, 13} (Visits must occur ± 7 days of scheduled visit; Every 4 weeks for 48 weeks)						Study Completion/ Early Withdrawal (Visit to occur 12 week ± week after last dose)	Survival Follow-up	
		2	3	4	5	6	7	8	9	10	11	12			
Visit	1	2	3	4	5	6	7	8	9	10	11	12			
Week	-1	1	4	7	10	12									
Timepoint (Day)	-28 to -1	1	22	43	64	78									
Research Procedures															
• Sample for immunogenicity ⁷		•			•							•	• 1 3	•	
• Serum for cytokine panel ⁷		•			•							•	• 1 3	•	
• Cellular immune assays ⁷		•			•							•	• 1 3	•	
• Cryopreserved serum ⁷		•			•							•	• 1 3	•	
• Tissue Submission ¹ 4		•	• ¹⁵	• ¹⁵	• ¹⁵	• ¹⁵	• ¹⁵	• ¹⁵	• 1 5		• ¹⁵				

Efficacy Procedures																	
CT/MRI (neck, chest, abdomen, pelvis) ^{9, 12}	•					•	•						•	•			
							1							1			
							4							4			
															•		•
CT/MRI (Brain)	•					•	•						•	•			
							1							1			
							4							4			•
Follow-up contact ¹⁰																	•
Study Drug Administration																	
Ipilimumab ¹¹		•	•	•	•												
Nivolumab ^{2,11}		•	•	•	•	• ¹³	•	•	•	•	•	•	•				

Key: CT = computed tomography, HIV = human immunodeficiency virus; ECOG = Eastern Cooperative Oncology Group; MRI = magnetic resonance imaging

FOOTNOTES:

- ¹Every effort should be made to infuse NIVOLUMAB in a 60-minute timeframe.
- ² The NIVOLUMAB dosage may be adjusted if there is a ± 10% weight change since the previous weight measurement only during cycle 1 Induction Treatment. No dose escalations or de-escalations are allowed during cycles 2-5 due to the use of flat dosing of NIVOLUMAB at 480 mg every 4 weeks. No dose escalations or de-escalations are allowed during cycles 2-5 due to the use of flat dosing of NIVOLUMAB at 480 mg every 4 weeks.
- ³ Informed consent must be signed before initiation of any study drug treatment or procedure. It may be signed more than 28 days before the first dose.
- ⁴ Pregnancy testing must be performed before any study drug is administered. The test result must be negative for a subject to receive study drug(s).
- ⁵ Vital signs will be monitored immediately prior to the NIVOLUMAB infusion; every 15 minutes during the 30 or 60-minute NIVOLUMAB infusion; and 15 and 30 minutes after completion of the NIVOLUMAB infusion. When slowing or re-starting the NIVOLUMAB infusion due to an infusion reaction/adverse event, vital signs should be monitored every 15 minutes or as directed by the Investigator until the infusion is completed, and 15 and 30 minutes after completion of the infusion and/or the subject is stabilized.
- ⁶ These evaluations are for baseline reference; subsequent evaluations may be performed if clinically indicated.

-
- ⁷ Sample to be drawn/collected pre-treatment at visits where 1 or more study drug will be administered. Hematology and serum chemistries for Cycle 1 Day 1 will not be re-drawn if screening labs were completed within 72 hours prior to study drug administration. This treatment group will draw amylase and lipase also.
- ⁸ CT neck will be done only in patients with prior disease in the head and neck
- ⁹ In patients who have not had disease progression, re-imaging should be performed every 6-12 months (minimum of every 12 months) for the first 2 years, then every 12 months (at the discretion of the treating physician) indefinitely or until progression.
- ¹⁰ Survival statuses for all patients who have discontinued from study treatment will be collected every 6 months (+/- 1 month) until death, lost to follow-up, or withdrawal of consent for survival follow-up. Follow-up contact may be done in person at the study center or by telephone; survival information may be obtained from family members or other medical professionals caring for the patient. Survival information including post-study treatment modalities and date and site of disease progression will be documented in the source documents and survival eCRF. Social security death index (SSDI) and other public records will be used if necessary to confirm survival status and/or date of death.
- ¹¹ There is only one 12 week induction treatment cycle (cycle 1). The ipilimumab will be at 1 mg/kg every 3 weeks for 4 doses during the 12 week induction cycle, and NIVOLUMAB will be at 3 mg/kg every 3 weeks for 4 doses during the 12 week induction treatment cycle then at 480mg every 4 weeks for 48 weeks during cycles 2-5.
- ¹² To be obtained every 12 weeks. Patients that discontinue therapy for any reason will only have the immunology procedures collected at the next mandated protocol timepoint, but not thereafter.
- ¹³ Radiology exams will be completed prior to dosing at week 12 and every 12 weeks prior to each dosing visit.
- ¹⁴ Tissue will be submitted, if available, as outlined in section 5.6.1
- ¹⁵ Tissue from any post-relapse biopsy will be requested for analysis by immunohistochemistry as outlined in section 5.6.1.

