
the results of that study.²² In the experience of 20 patients treated in cohort 4, 10 have had toxicity that precluded finishing 12 weeks of therapy, suggesting that for patients with resected stages 3C and 4 melanoma, the regimen of ipilimumab at 3 mg/kg and NIVOLUMAB at 1 mg/kg every 3 weeks for 4 doses may be difficult to tolerate, and suggesting that an alternative regimen of ipilimumab at 1 mg/kg and NIVOLUMAB at 3 mg/kg every 3 weeks for 4 doses was worthy of testing in cohort 5 at Moffitt. In that experience, 17 of the 20 patients treated were able to continue past the 12-week combination period. In that cohort, treatment was for 2 years with nivolumab alone after the 12-week induction with nivolumab and ipilimumab²³. In the current protocol, an additional 20 patients will be treated with the same doses as cohort 5 at Moffitt (ipilimumab 1/nivolumab 3) and the total duration of nivolumab treatment alone will be 1 year, in order to gather further feasibility and toxicity experience with this adjuvant regimen.

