1.6. Secondary Objectives

The secondary objectives of this study are to:

- evaluate the immune response to treatment with the study drugs at Week 12.
- assess the preliminary efficacy of the study drugs as defined by an assessment of time to relapse

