3.4.6 Early Discontinuation Criteria and Procedures

3.4.6.1 Discontinuation of Study Drug

It is the right and duty of the Investigator to discontinue the study drugs of any subject if he feels that discontinuation of the study drugs is necessary to protect the subject, or that there are unmanageable factors that may interfere significantly with the study procedures and/or the interpretation of results.

Administration of the study drugs will be discontinued if the subject develops a DLT, documented relapse, or other intolerability to the study drugs.

Administration of the study drugs may be discontinued during the study for any of the following reasons:

- Adverse event(s)
- Protocol violation
- Subject withdrew consent
- Lost to follow-up
- Other
- Death

For subjects who discontinue the study drugs for any reason, the remaining study visits and associated evaluations (without dosing) should be completed. Patients who discontinue the study drug(s) due to a toxicity will be followed until the toxicity resolves to baseline. Patients will continue to be followed on the protocol schedule for radiology assessments and for relapse free survival. Pharmacokinetic samples will only be collected at the visit following study drug discontinuation.

All subjects will be followed for adverse events for at least 70 days after the last dose of study drugs and for survival follow-up indefinitely until withdrawal of consent or death.

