5.6.3. Analysis of Immunological Response

For each time point (at baseline and Weeks 7 and 13) the percent of subjects with a response will be calculated – for T-cell proliferation response, along with an exact confidence interval.

Cryopreserved Serum

Serum samples will be analyzed to evaluate molecules that may be identified and implicated in regulating anti-melanoma immune responses and/or NIVOLUMAB/ipilimumab activity such as soluble MICA, and antibodies to melanoma antigens

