The four single nucleotide polymorphisms known to be present in CTLA-4 (79-81) and at least six known for PD-1 (82, 83) will be measured by DNA PCR analysis, and a selection of 20% of the total samples will have the results verified by direct DNA sequencing of the relevant areas of DNA. All subjects will be used from the first, and the second trials and the data will be pooled to allow correlations, if any, to be drawn between the presence of a SNP, response, time to progression and development of autoimmunity.

Studies on Regulatory T cells

We propose to study the regulatory activity of CD4⁺CD25⁺ ^{high} cells before and after NIVOLUMAB +ipilimumab treatment. Peripheral blood CD4⁺ T cells will be sorted into CD4⁺CD25⁺ and CD4⁺CD25⁻ populations by flow cytometry. The latter cell subset (responders) will be stimulated with anti-CD3 (10 µg/ml) alone or with anti-CD28 (2µg/ml) and with or without IL-2 (10 IU/ml) in the presence of increasing numbers of sorted CD4⁺CD25⁺ cells. In addition, CD4⁺CD25⁻ will be stimulated with allogeneic mature myeloid dendritic cells (DC), generated from PBMC with GM-CSF and IL-4 and matured with a cytokine cocktail (IL-6, IL-1 beta, TNF-alpha and PGE-2), in the presence or absence of

CD4⁺CD25⁺. The ability of CD4⁺CD25⁺ to suppress the proliferation of CD4⁺CD25⁻ to polyclonal or allogeneic stimulation in a 3 to 5 day proliferation assay using tritiated thymidine incorporation will be determined. We anticipate that CD4⁺CD25⁺ cells will exhibit suppressor activity in vitro as has been previously described and that NIVOLUMAB + ipilimumab treatment will inhibit their suppressive activity in either polyclonal or allogeneic proliferation reaction. We will examine whether loss of suppressor activity of CD4⁺CD25⁺ cells, if found, following NIVOLUMAB + ipilimumab treatment correlates with the development of colitis or other autoimmune side effects. The suppression of allo MLR proliferation by isolated CD4⁺CD25⁺ is an established assay, and well-established in the principal investigator group.

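### Table 1 footnote 12 ends immune sampling after drug is stopped, against the body text, and with three discordant immune schedules it can lose Week 12 samples from early stops

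*Combined protocol and SAP*

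**What the plan says.** **The objective.** The first secondary objective (section 1.6) is to "evaluate the immune response to treatment with the study drugs at Week 12". Section 6.3.4.1 fixes the definition of augmented T-cell proliferation at Week 12 as well.

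**The restriction.** Table 1, footnote 12, opens with "To be obtained every 12 weeks" and continues: "Patients that discontinue therapy for any reason will only have the immunology procedures collected at the next mandated protocol timepoint, but not thereafter".

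**The opposite rule.** Section 3.4.6.1 states: "For subjects who discontinue the study drugs for any reason, the remaining study visits and associated evaluations (without dosing) should be completed". The synopsis and section 2.1 say the same in substance. The only sampling that section 3.4.6.1 cuts back is pharmacokinetic, and section 5.4 excepts only infusions and pharmacokinetic samples. None of the four places exempts immunology.

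**The timepoints.** Section 5.6.2 sends the reader to Table 1 for the timing of research blood and to Appendix 4 for processing and handling. Section 5.6.3 nevertheless analyses other weeks: "For each time point (at baseline and Weeks 7 and 13) the percent of subjects with a response will be calculated"; section 6.3.4 uses the same weeks. Appendix 4 names pre-treatment, Weeks 5 and 9, and Week 12.

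**Missing results.** Section 6.4 has a general imputation rule with an adverse-event example. Nothing says how a missing Week 12 immune result is counted, and no denominator is defined for the response percentage.

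**The concern.** Footnote 12 is the only sentence that speaks specifically about immune samples after discontinuation. Study staff could reasonably follow it and stop drawing, or follow section 3.4.6.1 and continue. Blood that is not drawn cannot be recovered later.

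Any samples lost would not be a random subset. Dose-limiting toxicities are defined within 29 days of the first dose (section 4.2.4.1) and end treatment (sections 2.1 and 3.4.6.1). Patients withdrawn from the study in Cycle 1 for other reasons are replaced, but dose-limiting toxicity cases are not (section 4.9). Absence of a Week 12 sample could therefore depend on how the patient fared on treatment. Appendix 4 also asks whether loss of regulatory T-cell suppression after "treatment correlates with the development of colitis or other autoimmune side effects", and patients who stop early for such events are among those that question needs.

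The mixed model in section 6.3.4 can use baseline and interim values from patients who stop, provided the missing values are missing at random given what the model contains. The response percentage with its exact interval has no such protection.

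**Working it through.** There is no stated figure to reproduce: the sample-size text gives no expected immune response rate and no allowance for missing immune samples.

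**Step 1. What footnote 12 does under each schedule.** Take the first immune timepoint after the stop as the only further sample, and ask whether it is the end-of-induction sample.

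| Source of timepoints | Timepoints after baseline | Stops that lose the final sample |
|---|---|---|
| Table 1 as extracted | about Week 10 or Week 12 | none |
| Sections 5.6.3 and 6.3.4 | Weeks 7, 13 | before Week 7 (only Week 7 is drawn) |
| Appendix 4 | Weeks 5, 9, 12 | before Week 9 (only Week 5 or Week 9 is drawn) |

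The 29-day toxicity window ends at about Week 5. A patient stopped within it would lose the Week 13 or Week 12 sample under the second and third schedules, and would keep the end-of-induction sample under the first.

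Two cautions apply to the Table 1 line. The table is broken in the text available, so the "Cellular immune assays" mark cannot be fixed at Week 10 or Week 12. If it is Week 10, then Week 12 is unmarked for everyone, which is a separate defect. Also, the imaging row carries mark 12 and the immune rows carry mark 13, whose text concerns radiology. The markers may be shifted, and the 12-week interval in footnote 12 may refer to imaging.

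Appendix 4 has a difficulty of its own: it calls Weeks 5 and 9 infusion days, while Table 1 places induction infusions at Weeks 1, 4, 7 and 10.

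**Step 2. How many patients might stop early.** Section 1.4.3 reports for the predecessor cohort at the same induction doses that "17 of the 20 patients treated were able to continue past the 12-week combination period".

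- Not continuing: 20 − 17 = 3, and 3/20 = 15%.
- Clopper-Pearson 95% interval: lower limit is the 2.5% quantile of Beta(3, 18) = 3.2%; upper limit is the 97.5% quantile of Beta(4, 17) = 37.9%.
- Expected among 20 treated: 20 × 0.15 = 3 (20 × 0.032 = 0.6 to 20 × 0.379 = 7.6).

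The protocol does not say when or why those three stopped. Late stops keep the final sample, so the expected loss at the 15% rate is between 0 and 3 of 20.

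**Step 3. Effect on the response percentage.** With m of 20 samples missing and r responders among the 20 − m observed, the rate in all 20 lies between r/20 and (r + m)/20, a width of m/20.

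- m = 0: width 0.
- m = 3: width 3/20 = 15 points. For illustration, assume r = 8: observed 8/17 = 47%; bounds 8/20 = 40% and 11/20 = 55%.
- At the upper confidence limit, if every such patient stopped early enough to lose the sample: 7.6/20 = 38 points.

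**The case against.** The strongest reply is that footnote 12 belongs to Table 1, and section 5.6.2 makes Table 1 the sampling schedule. There, nothing is marked between Week 1 and about Week 10 or 12, so the next timepoint after any early stop is the end-of-induction sample itself and nothing is lost. This stands for Table 1. It does not settle the matter, because sections 5.6.3 and 6.3.4 plan to analyse other weeks and Appendix 4 plans to draw at others again.

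Table 1 also marks immune samples at the Study Completion/Early Withdrawal visit. That visit is required of patients who leave the study (section 3.4.6.2) and falls about 12 weeks after the last dose. It does not clearly cover a patient who stops drug and stays on study, and its timing is not Week 12.

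A further reply is that the body text already requires the samples. That is half of a contradiction, and nothing in the documents says which half prevails.

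A reader might infer three stronger things, and the documents support none of them:

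- **That Week 12 response is measured mainly in patients who tolerated induction because of the footnote.** With 17 of 20 continuing at these doses, most patients would be tolerators under any sampling rule.
- **That the result is biased downward.** The footnote covers stopping for any reason, relapse included. Early stoppers will have had fewer doses and may be on steroids at Week 12, so their values could be lower or higher than those of patients who continued.
- **That half the samples could go.** In predecessor cohort 4, 10 of 20 could not finish 12 weeks, but at ipilimumab 3 mg/kg with nivolumab 1 mg/kg, the reverse of this trial's 1 and 3 mg/kg.

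Nor is the regulatory T-cell question lost. It compares before with after treatment and names no week, so an early stopper still contributes baseline and one later sample.

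**Conclusion.** The contradiction is real and needs reconciling. Footnote 12 cannot be applied together with the synopsis and sections 2.1, 3.4.6.1 and 5.4, and its consequence depends on which of three immune schedules is meant.

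The size is modest: 0 to 3 of 20 end-of-induction samples at the predecessor rate, and up to 15 points between best-case and worst-case response percentages. This assumes that about 20 patients are treated, that the predecessor rate carries over, and, for the upper figure, that all three stops fall before the last interim sample. The 8 of 17 example is illustrative only.

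Any loss would be related to treatment outcome and could include the dose-limiting toxicity cases; the direction of bias is not known. The point should be fixed because the response percentage has neither a denominator nor a missing-data rule, and the remedy is cheap while samples can still be drawn.

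**What to change.** 1. Replace the second sentence of footnote 12 with a rule of this kind: the Week 12 immune blood sample is taken in every treated patient, whether or not study drug has been stopped, unless consent is withdrawn; a peripheral draw is acceptable. The synopsis and section 5.3 already allow peripheral draw as an alternative to leukapheresis.
2. Use one set of immune timepoints, including Week 12, in Table 1, sections 5.6.3 and 6.3.4 and Appendix 4, and check the footnote markers on the immune and imaging rows.
3. In section 5.6.3 or 6.3.4, define the Week 12 response percentage over all treated patients. Show missing samples by best-case and worst-case bounds, as in Step 3 of the working.
4. Record steroid use at each draw, and mark samples taken off drug or on steroids in the listings and summaries.

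The cost is a text amendment and a few extra draws, at visits section 3.4.6.1 already requires. The downside is that some samples will be taken on steroids and will be harder to interpret, which is why they need marking.
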